### 18.4 Definition of Evaluability

Endpoint	In order to be evaluable for this endpoint, a patient must...
Primary	
cCR at completion of short course radiation therapy and chemotherapy	Have completed the evaluation after completion of radiation therapy and chemotherapy.
Secondary	
Progression-free survival at 2 years	
Incidence of any grade $\geq 3$ toxicity during treatment	Have received at least one fraction of radiation therapy and one dose of chemotherapy.
Incidence of post chemoradiotherapy grade $\geq 3$ toxicity	
Anorectal function per FACT-C at 1 year	Have completed a FACT-C at baseline and at least one post-treatment time point.
1 and 2 year organ preservation rate	Have received at least one fraction of radiation therapy and one dose of chemotherapy.
Exploratory	
Associate tumor microenvironment with cCR and other clinical outcomes	Have tissue collected at baseline, received at least one fraction of radiation therapy and one dose of chemotherapy, and completed evaluation of their disease.
Associate ctDNA levels with cCR and other clinical outcomes	Have blood collected at baseline and at least one post-dose time point, received at least one fraction of radiation therapy and one dose of chemotherapy, and completed evaluation of their disease.

All eligible enrolled patients that receive any treatment will be included in the intention to treat analysis. Patients that complete protocol therapy (both radiation therapy and chemotherapy) as prescribed will be included in a per protocol analysis.

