### 18.5 Data Analysis

Demographic and clinical characteristics of the sample will be summarized using descriptive statistics. Primary endpoint of the cCR rate will be reported as a proportion with 95% confidence interval (CI), and a one-sided asymptotic Wald test will be performed

to compare the study cohort cCR rate to the null value of 30%. PFS is defined as the time from date of treatment to death or progression, which occurs first. The alive patients without progression are censored as the last date follow-up. Kaplan-Meier method will be used to calculate PFS at 2-year. Proportions of any grade  $\geq 3$  toxicity during treatment, of post chemoradiotherapy grade  $\geq 3$  toxicity and organ preservation rates at 1 and 2 year will be calculated. Their corresponding 95% CIs will also be provided. The quality of anorectal function as measured by the FACT-C questionnaire is collected at screening, completion of chemo, and 1 year after RT. The generalized estimating equation (GEE) model with appropriate link function will be used to analyze this longitudinal data, in which the correlation among the repeated measures from the same patient need be considered. The autoregressive of first order as working correlation structure will be used and the patients with missing values at any time points will be excluded from GEE analysis. Least square means for quality of anorectal function at 1 year after RT will be estimated and 95% CI calculated within the use of GEE sandwich method when accounting for within-patient correlation.

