## **18.6 FAK Expression and Tumor Microenvironment Analysis**

Rectal cancer biopsies will be assessed for total and phosphorylated FAK1 (Tyr-397, p-FAK1) and PYK2 (FAK2) by immunohistochemistry (IHC) as previously described. Rectal cancer samples will be stratified by high or low epithelial (tumor cell) p-FAK1 levels using IHC intensity and assessed for tumor-infiltrating CD3+, CD8+ cytotoxic T lymphocytes, neutrophil elastase and CD15+ granulocytes. Tumor fibrosis will be assessed by total collagen staining by Sirius Red and collagen I, III and IV deposition by IHC. Flow cytometry and IHC will be performed as previously reported. To investigate the relationship between tumor microenvironment (including FAK expression) or ctDNA levels with the outcomes of cCR, incidence of any grade  $\geq 3$  toxicity during treatment, incidence of post chemoradiotherapy grade  $\geq 3$  toxicity, and organ preservation rates, the logistic regression model will be considered. To investigate the relationship between tumor microenvironment (including FAK expression) or ctDNA levels with PFS, the Cox regression model will be considered. To investigate the relationship between tumor microenvironment (including FAK expression) or ctDNA levels with the outcomes of quality of anorectal function, the linear regression model will be considered.

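### The two biomarker rows of section 18.4 require a completed disease evaluation for every outcome, although only the association with cCR needs it

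*Combined protocol and SAP*

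**What the plan says.** The evaluability table in section 18.4 has one row for each exploratory marker objective.

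- **Tissue row:** "Have tissue collected at baseline, received at least one fraction of radiation therapy and one dose of chemotherapy, and completed evaluation of their disease".
- **ctDNA row:** "Have blood collected at baseline and at least one post-dose time point, received at least one fraction of radiation therapy and one dose of chemotherapy". It closes with the same condition as the tissue row: "one dose of chemotherapy, and completed evaluation of their disease". Its objective is worded "Associate ctDNA levels with cCR and other clinical outcomes", so one rule serves every outcome.
- **Secondary rows, same table:** toxicity during treatment and organ preservation carry the shorter rule "Have received at least one fraction of radiation therapy and one dose of chemotherapy". No disease evaluation is asked for.
- **Primary row:** the cCR rule is "Have completed the evaluation after completion of radiation therapy and chemotherapy".

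Section 18.6 then relates the markers to cCR, both toxicity endpoints and organ preservation by logistic regression, and to anorectal function by linear regression. For PFS it says "or ctDNA levels with PFS, the Cox regression model will be considered". It defines no analysis set of its own. Section 18.5 fixes the time origin: "PFS is defined as the time from date of treatment to death or progression, which occurs first".

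**The concern.** A completed disease evaluation is a sensible condition for cCR, which cannot be scored without one. For the other outcomes it is a condition on something that happens after baseline. Death, progression and grade 3 or higher toxicity are recorded on event-driven or ongoing forms (section 14) and do not need the evaluation.

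PFS is counted from treatment start, but entry to the marker analysis depends on what happens during the months being counted. A patient who dies on treatment has baseline tissue, a dated PFS event and a grade 5 toxicity record, and is still outside the marker models. The same patient can be counted for the toxicity endpoint and excluded from the marker model of that endpoint.

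Section 1.5 motivates the markers by treatment resistance and poorer survival, so early failures are informative cases. With few PFS events expected in 63 patients, avoidable losses deserve attention.

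**Working it through.** **1. No figure to reproduce for this analysis.** The plan gives no sample size, event count or power for the marker models. Its only design figure is the two-stage test of cCR (8/24, then 25/63). That reproduces: exact one-sided alpha 0.0497 and power 0.903. The marker rows do not affect it.

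**2. When the evaluation falls.** The marker rows give no date. Sections 5.2, 5.3 and 14 schedule one mandatory post-baseline disease evaluation before follow-up, 3-8 weeks after chemotherapy; the MRI 8 weeks after radiotherapy is optional. Inputs are radiotherapy 1-2 weeks (6.1), gap 2-4 weeks, chemotherapy 15 weeks (CAPOX) or 16 weeks (FOLFOX), and permitted delay up to 4 weeks (7.1).

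- Earliest: 1 + 2 + 15 + 3 = 21 weeks (4.8 months).
- Latest without delay: 2 + 4 + 16 + 8 = 30 weeks (6.9 months).
- With the permitted delay: 30 + 4 = 34 weeks (7.8 months).

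That is 20% to 33% of a 24-month PFS window.

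**3. Events at risk of being lost.** The documents state no PFS rate, so 2-year PFS of 80% or 70% with constant hazard is an assumption. Month 6 stands for the evaluation. Expected events are 63 × (1 − S), and those before month 6 are 63 × (1 − S^(6/24)).

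| Assumed 2-year PFS | Events by 2 years | Before month 6 | Left if all are lost | Left if 25% are lost | Left if 10% are lost |
|---|---|---|---|---|---|
| 80% | 12.6 | 3.4 | 9.2 | 11.7 | 12.3 |
| 70% | 18.9 | 5.4 | 13.5 | 17.6 | 18.4 |

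**4. Power for a 50:50 baseline marker, constant hazard ratio 3.** Schoenfeld approximation: power = Φ(½ √D × ln 3 − 1.96), where D is the number of events.

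- 80% PFS: 0.50 with all events, 0.49 with 10% of early events lost, 0.47 with 25% lost, 0.38 with all lost.
- 70% PFS: 0.67, 0.65, 0.63 and 0.52 in the same order.

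Cox simulation of 63 patients at 70% PFS gives lower absolute power and the same pattern: 0.57 in full, 0.56 with 10% lost and 0.55 with 25% lost, the estimated hazard ratio staying at about 3.0-3.1. With all early events lost, simulated power is 0.43-0.44, against 0.59 for the full set in those runs.

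**5. Bias in the hazard ratio.** Large-sample Cox fits (80% 2-year PFS in marker-negative patients), full set against the set without any event before month 6:

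- Constant ratio 2: 1.93 against 1.91.
- Ratio 3 before month 6 and 1.5 after: 1.87 against 1.48.
- Ratio 3 before and 1 after: 1.61 against 1.07.

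In a strongly front-loaded scenario (5 before, 1.5 after; 63 patients, 70% PFS), the median estimate goes from 2.50 to 2.42 with 10% of early events lost, 2.35 with 25%, about 2.1 with half and 1.5 with all. Power falls faster there than under a constant ratio, because the dropped events carry the effect.

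**6. Toxicity.** Assume grade 3 or higher rates of 30% (marker-negative) and 50% (marker-positive). The true odds ratio is (0.5/0.5)/(0.3/0.7) = 2.33.

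- If 20% of patients with toxicity and 5% without are never evaluated, whatever their marker, both odds are multiplied by 0.80/0.95 and the ratio stays 2.33.
- If the share lost after toxicity is 10% in marker-negative and 30% in marker-positive patients (5% without toxicity in both), it becomes 2.33 × 0.70/0.90 = 1.81. With 40% in marker-positive patients it is 2.33 × 0.60/0.90 = 1.56.

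**The case against.** The strongest reply is that the rule removes few people.

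- **The wording does not name the post-chemotherapy visit.** The primary row does; the marker rows do not. Any post-baseline evaluation might satisfy them. This stands as a limit on reach. A baseline-only reading would make the condition almost empty, so some later evaluation is the natural meaning, but the text leaves it undefined.
- **Stopping chemotherapy excludes no one.** A reader might infer that every patient who ends treatment early for toxicity leaves the marker set. The documents do not support that: section 8.2 keeps patients on study when a drug is dropped, and stopping does not prevent a later MRI, endoscopy or digital examination.
- **Most early progression would be found by an evaluation.** No disease imaging is mandatory between baseline and the post-chemotherapy visit, so progression will mostly be detected there or later, or by an unscheduled evaluation that could itself meet the rule. This largely stands. The clear losses are deaths and withdrawals with no evaluation, in patients with M0 disease and performance status 0-2.
- **The intention-to-treat sentence under the table covers all eligible treated patients.** It does not say which endpoints it governs and does not override the marker rows, so it does not resolve the point.
- **The analyses are exploratory.** The study is not powered even for secondary endpoints, and the section 18.6 models are only to be considered. This stands and sets the severity.

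**Conclusion.** The point holds as a minor defect. A condition suited to cCR is written into the marker analyses of PFS, toxicity and organ preservation. Followed literally, it removes treated patients who have a baseline marker, and possibly a recorded event, but no post-baseline disease evaluation.

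The likely cost is some early events and some precision. The upper bound is every event before month 6: 12.6 to 9.2 at an assumed 80% 2-year PFS. If 10-25% of early events lack an evaluation, the loss is 0.3-0.9 of an event at 80% PFS (0.10 × 3.4 to 0.25 × 3.4), and power under a constant hazard ratio changes by about 0.01-0.03. The PFS rates, the share without an evaluation, the 50:50 marker and the hazard ratios are all assumptions; none is in the documents.

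A reader might infer that the marker hazard ratios will be pulled well toward 1. The documents do not support this. It would need a marker effect concentrated early, which section 1.5 does not claim, or dropout that depends on both marker and outcome, together with a substantial share of early events never evaluated. Under a constant hazard ratio the estimate is nearly unchanged. The primary test and the secondary endpoint estimates are not affected.

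**What to change.** Reword the two exploratory cells of section 18.4 by outcome:

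- **cCR:** keep the completed-evaluation condition, and say which evaluation is meant.
- **PFS, toxicity and organ preservation:** use the endpoint's own evaluability set plus an available baseline marker, counting events from treatment start whether or not a later evaluation took place.
- **FACT-C:** require the relevant questionnaires.
- **ctDNA:** keep the post-dose blood requirement only for analyses that use post-baseline ctDNA.

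Add a sentence to section 18.6 pointing to these sets. No new data are needed, since progression, death and adverse events already have their own forms. The cost is that marker analysis sets differ slightly between outcomes, so each table should report its own number of patients and events.

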### 18.5 Data Analysis

Demographic and clinical characteristics of the sample will be summarized using descriptive statistics. Primary endpoint of the cCR rate will be reported as a proportion with 95% confidence interval (CI), and a one-sided asymptotic Wald test will be performed

to compare the study cohort cCR rate to the null value of 30%. PFS is defined as the time from date of treatment to death or progression, which occurs first. The alive patients without progression are censored as the last date follow-up. Kaplan-Meier method will be used to calculate PFS at 2-year. Proportions of any grade  $\geq 3$  toxicity during treatment, of post chemoradiotherapy grade  $\geq 3$  toxicity and organ preservation rates at 1 and 2 year will be calculated. Their corresponding 95% CIs will also be provided. The quality of anorectal function as measured by the FACT-C questionnaire is collected at screening, completion of chemo, and 1 year after RT. The generalized estimating equation (GEE) model with appropriate link function will be used to analyze this longitudinal data, in which the correlation among the repeated measures from the same patient need be considered. The autoregressive of first order as working correlation structure will be used and the patients with missing values at any time points will be excluded from GEE analysis. Least square means for quality of anorectal function at 1 year after RT will be estimated and 95% CI calculated within the use of GEE sandwich method when accounting for within-patient correlation.

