### **18.2 Study Design and Sample Size Justification**

The purpose of this phase II study is to determine if the cCR of short course radiation therapy followed by multiple agent chemotherapy in rectal adenocarcinoma is at least 50% in a multi-institution setting. Given that less than one-third of patients with cCR is deemed as an ineffective therapy clinically, our null hypothesis is that cCR rate is 30%. Our phase 1 data indicated a 74% cCR rate but our retrospective study showed 50%, which is more representative of advanced stage and all patients. Therefore, a cCR rate of 50% was considered in the alternative hypothesis. A Simon two-stage design with a 90% power at one-sided 5% type I error will be used to test the null hypothesis. At the first stage, we will enroll 24 patients. If the study continues, 39 additional patients will be needed. Study is not powered for secondary endpoints.

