### 18.3 Interim Analyses and Stopping Rules

An interim analysis will be performed on the primary endpoint once 24 subjects have been enrolled and have completed the evaluation after chemotherapy. If  $\leq 8$  patients have cCR in these 24 patients, the study will be stopped for futility. Otherwise, the additional 39 patients will be enrolled. The null hypothesis will be rejected if  $\geq 25$  patients with cCR are observed in 63 patients.

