## APPENDIX F: STUDY SPECIFIC DSM TABLES

Protocol Objectives and Subject Evaluability	
Objective	# of patients evaluable for this endpoint to date
Primary	
To determine the clinical complete response rate (cCR) rate of patients with stage I-IIIB (cT1-3, N0-2a, M0) rectal cancer being treated with sequential short course radiotherapy followed by multi-drug chemotherapy.	
Secondary	
To determine the 2 year progression free survival (PFS)	
To determine the incidence of any grade $\geq 3$ toxicity during treatment.	
To determine the incidence of post chemoradiotherapy grade $\geq 3$ toxicity at 1 year	
To determine quality of anorectal function at 1 year using the FACT-C questionnaire.	
To determine the 1 and 2 year organ preservation rate	
Exploratory	
To associate tumor microenvironment (including FAK expression) with cCR and other clinical outcomes.	
To associate ctDNA levels with cCR and other clinical outcomes.	

Interim Analysis and Early Stopping Rules	
Does the study design include an interim toxicity analysis?	
No	
Does the study design include an interim futility analysis?	
Yes	
If yes, describe.	An interim analysis will be performed on the primary endpoint once 24 subjects have been enrolled and have completed the evaluation after chemotherapy. If $\leq 8$ patients have cCR in these 24 patients, the study will be stopped for futility. Otherwise, the additional 39 patients will be enrolled. The null hypothesis will be rejected if $\geq 25$ patients with cCR are observed in 63 patients.
Has the interim futility analysis been conducted?	
If yes, describe the results of the interim futility analysis.	
Are there early stopping rules that outline circumstances under which the study must be suspended or closed?	
Yes	
If yes, describe.	If $\leq 8$ patients have cCR in the first 24 patients, the study will be stopped for futility.

Provide data describing whether the stopping rules have been met.

Response Data					
UPN	Subject Site	On tx date	# of cycles completed	Pt replaced?	Best response

Aggregated Response Data							
Response	Completion of Chemo	Non-operative patients only					
		3 mon	6 mon	9 mon	12 mon	16 mon	24 mon
cCR							
PR							
SD							
PD							
NE							

Treatment Discontinuation and Survival				
UPN	Date off tx	Reason off tx	Vital status	If dead, cause

Summary of Specimen Collections			

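### Section 18.5 tests the primary endpoint with a single-stage Wald test that, in its usual form, does not reject at 25/63, the count at which sections 18.3 and Appendix F reject; the plan does not say which rule governs

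*Combined protocol and SAP*

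**What the plan says.** Section 18.2 sets the hypotheses: "our null hypothesis is that cCR rate is 30"%, and "a cCR rate of 50% was considered in the alternative hypothesis". It states that a Simon two-stage design "with a 90% power at one-sided 5% type I error will be used to test the null hypothesis". Stage 1 is fixed there too: "At the first stage, we will enroll 24 patients", followed by 39 more if the study continues.

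Section 18.3 gives the decision rule. The trial stops for futility if 8 or fewer of the first 24 patients have a cCR. The null is rejected if at least 25 "patients with cCR are observed in 63 patients". Appendix F repeats both parts: "Otherwise, the additional 39 patients will be enrolled. The null hypothesis will be rejected if" the count reaches 25 of 63.

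Section 18.5, which describes the analysis of the primary endpoint, says the rate will be given as a proportion with a 95% CI, "and a one-sided asymptotic Wald test will be performed" "to compare the study cohort cCR rate to the null value of 30"%. It does not refer to the two stages, the 25/63 boundary or any adjustment for the interim look. It also does not give the variance form, scale or level of the Wald test.

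**The concern.** The plan has two tests of one null hypothesis for its primary endpoint. One is an exact two-stage counting rule. The other is a large-sample, single-stage test. They need not agree at the boundary, and nothing says which one decides or that either is only descriptive.

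If the final count were 25/63, an analyst following 18.5 with the usual Wald statistic would report a primary p-value above 0.05, next to a rule in 18.3 and Appendix F that calls the same result a rejection. The conclusion could then turn on a choice of test, or of variance form, made after the count was known.

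Separately, at every count reached in stage 2, the 18.5 p-value takes no account of the futility look, and 18.5 asks for no two-stage adjustment of the CI.

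**Working it through.** **Inputs.** Null rate 0.30, alternative 0.50, one-sided level 5%, power 90%, stage 1 n = 24, stage 2 n = 39 (section 18.2). Stop if ≤8/24, reject if ≥25/63 (section 18.3 and Appendix F). One-sided asymptotic Wald test against 0.30 (section 18.5). Section 18.5 does not restate the level, so one-sided 5% (critical value 1.645) is carried over from 18.2.

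**1. Reproduce the stated design.** With X1 ~ Bin(24, p) and X2 ~ Bin(39, p),

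P(reject) = Σ over x1 = 9 to 24 of P(X1 = x1) × P(X2 ≥ 25 − x1).

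- p = 0.30: 0.0497
- p = 0.50: 0.903

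The stated 5% and 90% are met. A full search shows this is the Simon optimal design for these inputs. The probability of stopping early under the null is 0.725.

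**2. Usual Wald test at the boundary** (variance at the observed rate): z = (p̂ − 0.30) / √(p̂(1 − p̂)/63).

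- 25/63: p̂ = 0.3968; z = 0.0968 / √(0.3968 × 0.6032 / 63) = 0.0968 / 0.0616 = 1.571; p = 0.058. Not rejected.
- 26/63: p̂ = 0.4127; z = 0.1127 / 0.0620 = 1.817; p = 0.035. Rejected.

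**3. Other forms at 25/63.**

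| Form | One-sided p | Rejects at 5%? |
|---|---|---|
| Wald, variance at observed rate | 0.058 | No |
| Null variance (strictly the score test): 0.0968 / √(0.3 × 0.7 / 63) = 1.677 | 0.047 | Yes |
| Wald on the logit scale, z = 1.664 | 0.048 | Yes |
| Wald, continuity-corrected | 0.075 | No |
| Single-stage exact binomial | 0.064 | No |
| Exact two-stage (step 1 at p = 0.30) | 0.0497 | Yes |

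All of these reject at 26/63 and none rejects at 24/63, so the disagreement is at one count only.

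**4. Operating characteristics if the usual Wald test decided.** The rule becomes ≥26/63 after continuing at stage 1. The sum in step 1 with 26 in place of 25 gives type I error 0.031 and power 0.885.

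**5. Chance of landing on exactly 25/63.** This is the difference between the two rejection probabilities.

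| True rate | P(exactly 25/63) | P(continue) | Given stage 2 is reached |
|---|---|---|---|
| 30% | 0.0497 − 0.0308 = 0.019 | 0.275 | 6.9% |
| 40% (illustrative, not in the plan) | 0.072 | 0.672 | 10.7% |
| 50% | 0.9033 − 0.8846 = 0.019 | 0.924 | 2.0% |

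**6. Intervals at 25/63.** The Wald 95% CI is 0.3968 ± 1.96 × 0.0616, or 27.6% to 51.8%. For the exact two-stage interval, the lower limit solves P(continue and total ≥25) = a, and the upper limit solves P(stop) + P(continue and total ≤25) = a. With a = 0.025 it is 28.2% to 56.1%. With a = 0.05 (a 90% interval) it is 30.02% to 53.5%. The 90% interval excludes 30%, as the one-sided 5% test does. The 95% interval includes it.

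**The case against.** The strongest reply is that the plan contains only one decision rule. Section 18.2 assigns the test of the null to the Simon design, and 18.3 and Appendix F both give an integer rejection boundary. Section 18.5 gives no level, critical value or rejection criterion and can be read as describing what will be reported. On that reading, 18.5 lacks only a cross-reference. Moreover, the tests differ at one count, whose probability is 1.9% at each rate the plan specifies. The interim look is for futility only, so an unadjusted final test does not inflate type I error. Nor is the mismatch special to the Wald test, since a single-stage exact test also fails to reject at 25/63.

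Much of this stands. The Simon rule is probably the one intended, the effect is small, and the error rate is protected. It is also fair that 18.5 does not yield a unique p-value, because two other forms agree with 18.3.

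That last point shows what is missing, however. At the plan's own boundary, an unstated choice of variance or scale settles whether the primary p-value falls below 0.05. The usual meaning of a Wald test puts it above. Section 18.5 says the test will be performed against the null value and does not call it descriptive. The likely intent should be written down.

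One further caveat is fair: section 18.4 defines evaluable, intention-to-treat and per-protocol sets, whose size may differ from 63. The figures here apply to exactly 63 analysed patients.

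**Conclusion.** The concern holds. Section 18.5 prescribes a test of the primary hypothesis that ignores the two-stage design and, in its usual form, contradicts 18.3 and Appendix F at exactly 25/63 (p = 0.058 against an exact two-stage p of 0.0497). The plan gives no order of precedence.

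The size is modest. Only one count is affected. Were the Wald test decisive, power would fall from 0.903 to 0.885, slightly below the stated 90%, and type I error would fall from 0.0497 to 0.031. The sample size and interim rule are sound.

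The conclusion rests on three assumptions: the Wald variance is taken at the observed rate, the one-sided 5% level of 18.2 applies, and exactly 63 patients are analysed. It should be fixed because it concerns the primary conclusion and the remedy is simple.

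**What to change.** In section 18.5:

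1. State that the primary conclusion follows the section 18.3 rule: continue if ≥9/24, reject the null if ≥25/63 (exact type I error 0.0497, power 0.903).
2. Replace the Wald test with the exact two-stage p-value. If the Wald p-value is kept, name its variance form, label it descriptive and say that it does not decide the primary endpoint.
3. Report the cCR rate with a CI that accounts for the two stages. Note that a two-sided 95% interval is stricter than the one-sided 5% test and can include 30% at the boundary.

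The first sentence alone resolves the conflict; the other two bring the reported p-value and interval into line with the design. The cost is wording only: no extra patients or data, and no change to the sample size or the futility rule. The change should be made before the final primary analysis, so that the choice of test cannot appear to depend on the result.

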#### **5.4 Follow-up**

The FACT-C questionnaire and follow-up visit will be done 10-14 months from treatment (radiotherapy) start date.

Patients undergoing nonoperative management will be assessed for sustained cCR by rectal protocol MRI pelvis, endoscopy (sigmoidoscopy preferred, rigid proctoscopy accepted) and DRE every three months (not necessarily on the same day / appointment) for 1 year then every 3-4 months for the second year. If patient is unable to receive an MR pelvis every 3 months, every 6 months is acceptable as long as endoscopic exam is performed as per protocol schedule. CT chest and abdomen with contrast is to be obtained every 6 months for the first 2 years. Each of the follow-up studies and visits have a permitted variation of  $\pm 2$  weeks. After 2 years of follow-up on study, we recommend off-protocol follow-up with the same studies every 4-6 months per treating physician discretion.

Once a patient undergoes surgical resection they will undergo imaging and surgical follow-up as per institutional standard of care. These patients will continue to be followed for data collection for during study follow-up.

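### PFS is censored at last follow-up, a date not tied to any disease assessment, so 2-year PFS can be biased upward where contact outlasts examination

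*Combined protocol and SAP*

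**What the plan says.** Section 18.5 defines the endpoint ("PFS is defined as the time from date of treatment to death or progression, which occurs first"), the censoring ("The alive patients without progression are censored as the last date follow-up") and the estimator ("Kaplan-Meier method will be used to calculate PFS at 2-year"). It does not define the last follow-up date, and no other section gives a PFS censoring rule.

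Section 5.4 sets the examinations. For the non-operative group: "Patients undergoing nonoperative management will be assessed for sustained cCR by rectal protocol MRI pelvis, endoscopy" and digital rectal examination (DRE), three-monthly in year 1 and every 3 to 4 months in year 2. There is a relaxation for MRI ("If patient is unable to receive an MR pelvis every 3 months, every 6 months is acceptable"), on condition that endoscopy stays on schedule. For distant disease: "CT chest and abdomen with contrast is to be obtained every 6 months for the first 2 years". After surgery the protocol schedule ends: "Once a patient undergoes surgical resection they will undergo imaging and surgical follow-up as per institutional standard of care". Data collection does not end: "These patients will continue to be followed for data collection for during study follow-up".

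Three other places matter:

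- Section 14 limits the scheduled Follow-Up Form (months 3 to 24) to patients without surgery. The last scheduled Disease Assessment Form falls 3 to 8 weeks after chemoradiation. The progression and death forms are completed only when the event occurs.
- Section 13 lists history and physical, ctDNA and FACT-C for the 10-to-14-month visit, but no endoscopy, DRE or imaging.
- Section 15 defines progression as growth of the primary by RECIST or new metastases.

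**The concern.** A patient can be recorded as progression-free only up to the last time someone looked for disease. Contact by itself does not establish whether the primary has grown or metastases have appeared. If the censoring date is a later contact, Kaplan-Meier keeps the patient in the risk set over a period in which progression would not have been seen. The denominator is then too large for the events that could be counted, and the survival estimate is too high.

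Two-year PFS is the first secondary objective, and Section 2 justifies it as the check on recurrence, metastasis and death under a new treatment approach. The trial has one arm, so no comparator shares the error. The same event times would presumably enter the exploratory Cox models in Section 18.6.

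**Working it through.** **1. The plan's own figures.** The documents give no assumed 2-year PFS, no expected rate of missed assessments and no precision for PFS; Section 18.2 says the secondary endpoints are not powered. The only design calculation is the Simon design for cCR: 24 + 39 = 63 patients, stop at 8 or fewer of 24, reject at 25 or more of 63. Exact binomial calculation gives a one-sided type I error of 0.0497 at 30% and power of 0.9033 at 50%, so the stated 5% and 90% reproduce. The calculation uses cCR counts only and does not depend on the PFS rule.

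**2. Who is exposed.**

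- *Non-operative, on schedule.* Radiotherapy takes 1 to 2 weeks, the interval to chemotherapy is 2 to 4 weeks, chemotherapy lasts 15 to 16 weeks, and up to 4 weeks of delay are allowed. Chemotherapy therefore ends between 1 + 2 + 15 = 18 and 2 + 4 + 16 + 4 = 26 weeks from treatment start, about 4 to 6 months. If clinic follow-up is counted from the end of chemotherapy, as Section 11.2 does for ctDNA (an assumption for the clinic visits), month 24 falls about 28 to 30 months from treatment start. These patients are examined past the 2-year landmark and add essentially no bias.
- *Resected.* They have no protocol imaging schedule and no Follow-Up Form, and the 10-to-14-month visit can be their latest protocol contact. If cCR is 50% and every non-responder has surgery (an assumption), this is up to 63 × 0.50 ≈ 32 patients. They are still examined under local practice, so this is the number at risk of a gap, not the number with one.
- *Missed assessments with continued contact.* The documents give no number.

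**3. Upper illustration.** Assume a constant hazard, S(24) = 0.70, a share f last examined at month t but followed to month 24, and no event recorded after t in those patients. Then

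reported PFS = (1 − f) × 0.70 + f × S(t), with S(t) = 0.70^(t/24).

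S(12) = 0.70^0.5 = 0.8367 and S(18) = 0.70^0.75 = 0.7653. For example, f = 0.40 and t = 12 gives 0.60 × 0.70 + 0.40 × 0.8367 = 0.755.

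| f | last examined at 12 months | last examined at 18 months |
|---|---|---|
| 10% | 71.4% (+1.4) | 70.7% (+0.7) |
| 25% | 73.4% (+3.4) | 71.6% (+1.6) |
| 40% | 75.5% (+5.5) | 72.6% (+2.6) |

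**4. Simulation of both rules.** Settings: 63 patients, 600 replicates per scenario, true 2-year PFS of 60%, 70% or 80%, and events dated at the detecting assessment. A share f stops being assessed at one of five times between 5.5 and 17.5 months. Contact continues for 3 months, 6 months, or to the end of follow-up at 29.5 months. Stopping is unrelated to outcome, and events in the gap go unrecorded. All of these are assumptions. The estimate under last-follow-up censoring minus that under last-assessment censoring was:

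- f = 0: 0.0 points
- f = 10%: +0.2 to +1.9 points
- f = 25%: +0.5 to +4.6 points
- f = 50%: +1.1 to +9.2 points

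Last-assessment censoring stayed within about 1 point of the true value throughout.

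**5. Scale.** The 95% half-width at 70% with 63 patients and no early censoring is 1.96 × √(0.70 × 0.30 / 63) = 0.113, about 11 points.

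**The case against.** The strongest reply is that the plan says last follow-up, not last known alive. For non-operative patients a follow-up visit is a disease assessment: the Follow-up column in Section 13 holds endoscopy, DRE, imaging and staging. The two dates then nearly coincide and the bias is close to zero. This stands, and it limits the point to the groups named above.

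A reader might also infer that 6-monthly CT, or the 6-monthly MRI option, creates a gap in every patient. The documents do not support that for local disease, because reduced MRI is allowed only while endoscopy stays on schedule. For distant disease a visit can follow the last CT by some months, but a rule that accepts any single examination would leave that interval unchanged.

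The illustrated sizes are a ceiling. Deaths are PFS events with their own form, and clinically evident progression is reported when it occurs, so part of what the formula treats as missed would be captured. PFS is secondary, unpowered, and tied to no threshold or stopping rule. Both points stand.

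Finally, changing the censoring sentence alone could do harm. No scheduled form records a negative examination after resection, so resected patients might be censored near surgery. Many would be non-responders, and that censoring could be informative. This stands as well, and the fix has to deal with it.

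The reply does not remove the central gap: the date is undefined, and for resected patients nothing in the plan ties it to an examination.

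**Conclusion.** The concern holds as a possible bias, not a demonstrated one. The rule in Section 18.5 allows unexamined time to count as progression-free, and where that happens the 2-year PFS is pushed upward. A reader might go further and conclude that the reported PFS will be inflated. The documents do not support this: with no gap between contact and examination the difference is zero, and they do not show how often a gap will occur.

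The size cannot be determined from the documents. With true 2-year PFS of 70%, constant hazard and no gap events recorded, it is about 0.7 to 1.4 points at 10% affected and 2.6 to 5.5 points at 40%. These excesses are smaller than the sampling half-width of about 11 points but, unlike sampling error, run in one direction. The primary cCR test and the Simon design are not touched. The rule should be changed because the change is cheap and PFS is the first-listed secondary endpoint.

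**What to change.** In Section 18.5:

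- Censor patients alive without progression at the date of their last adequate disease assessment that showed no progression.
- State which examinations count. Local: endoscopy with DRE, or pelvic MRI. Distant: CT or an equivalent staging study. After resection: institutional surveillance imaging or examination. Say also whether one type is enough or both local and distant are needed.
- Report last-follow-up censoring as a sensitivity analysis. Last-assessment censoring assumes that stopping assessment is unrelated to outcome, so the two results should be read together.

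In Section 14, record the date and result of the last such assessment for resected patients, within the data collection that already continues under Section 5.4. Without this item the new rule should not be adopted for them.

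The cost is a few sentences and one extra data item for resected patients, with no added visits or tests. Follow-up time will be slightly shorter, and the PFS estimate slightly wider and possibly less favourable.
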